## 9.7.3.6 Methods of Analysis for Health Resource Used Related (HRUR) Endpoints

All HRUR parameters will be summarized by treatment regimen (on-demand, prophylaxis). If available, changes from baseline to each follow-up study visit will summarized by treatment regimen. Below is list of all HRUR parameters:

- Health resource use: number of visits at the site
- Unscheduled visits at the site
- Number of hospitalizations related to haemophilia (surgery excluded)
- Length of stay in hospital per stay
- Antiphlogistic drug use
- Infusion log for FEIBA NF
- Acute pain associated with haemophilia, as measured with individual bleeding episodes, using the NRS or the Wong Baker Face Scale in pediatric subjects
- Chronic pain will be assessed on annual basis or more frequently based on current standard at the centre at the screening visit, on each annual visit and at the termination visit by using the NRS or the Wong Baker Face Scale in pediatric subjects
- Number of days lost from school or work due to bleeding episodes or their treatment
- Concomitant medications /Non-drug therapies
- Duration of infusion of FEIBA NF (reconstitution time excluded)

## 9.7.3.7 Methods of Analysis Pharmacodynamic (TGA) Endpoints

Descriptive statistics and figures will be computed by treatment regimen (on-demand, prophylaxis) to assess the pharmacodynamic responses from TGA parameters over the course of the study. Means (SD), medians (IQR), first quartile, third quartile, 95% confidence intervals of point estimates, maximum, and/or minimum will be generated. There will be no formal statistical comparison conducted. TGA parameters will include peak thrombin [nmol/l], endogenous thrombin potential (ETP, area under the curve) [nmol\*min/L], onset time (time to the start of observable thrombin generation) [minutes], and peak time (time to reach the peak thrombin) [minutes].

The association between TGA parameters and bleed rates, total dose (U/kg), and the number of infusions for bleeding treatment will be evaluated using a non-parametric Spearman's correlation coefficient by independent treatment regimens (on-demand and prophylaxis).

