- The FEIBA GO study will also allow to collect data from routine clinical practice on larger number of inhibitor patients regarding health resource use, quality of life, number of days lost from school or work due to bleeding episodes, and the possible correlation between TGA and clinical outcome.
- The FEIBA GO study may also help to identify subgroups of patients that can benefit most from prophylaxis treatment, which is of great importance in a complex clinical situation such as the presence of high responding inhibitors to FVIII or FIX in haemophilia patients.
- The FEIBA GO study will also allow to collect safety data from routine clinical practice regarding the safety of FEIBA NF and to explore the possible difference in safety profile of FEIBA used on-demand vs. prophylactically

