## 9.3.4 Pharmacodynamic Variables

- Individual pharmacodynamic properties (PD) of FEIBA NF by thrombin generation assay (TGA), if available
  - TGA measures the thrombin concentrations before and after clot formation and it is very sensitive to variations in individual or groups of coagulation factors. *In vitro* spiking of high-titre inhibitor plasma with increasing concentrations of FEIBA NF resulted in the dose-dependent restoration of the thrombin-generating capacity of the FVIII-inhibitor plasma. It has been reported  that defective thrombin generation is reversed in patients with FVIII inhibitors within 30 min after a single injection of therapeutic doses of FEIBA NF. The changes in the kinetics of thrombin generation measured before, during and after FVIII-bypassing therapy reflect the pharmacological effect of the drug. TGA may enable the pharmacodynamic and pharmacokinetic properties of bypassing therapies to be monitored, thus helping to optimize treatment, however, more data on clinical efficacy in relation with TGA are needed 
  - ➤ Thrombin generation (TG) can be used to individualize FEIBA NF treatment as a component of overall coagulation monitoring for major surgeries 
  - Assessments from TGA [peak thrombin (nmol/L), ETP (area under the curve), lag time (time to start of observable thrombin generation), velocity index (nmol/L\*min) and time to thrombin generation peak (min)] will be summarized for subjects with available data. Time points of blood collection and the method used for TGA execution will be collected and analysed. Date/time of the last FEIBA infusion, total units given (U), body weight (kg) at time of infusion, pre and post-infusion blood draws), the laboratory where TGA was assessed, and reason of infusion (i.e., to assess TGA) will be recorded

The association between these parameters and bleeding rates, bleeding treatment efficacy and overall effectiveness, total dose (U/kg), and the total number of infusions for bleeding will be evaluated (treatment will be evaluated using a non-parametric Spearman's correlation coefficient, for both prophylaxis and on-demand treatment).

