## 9.7.3.1 Primary Endpoint

The primary endpoint, the ABR of all types of bleeding episodes, will be calculated for each subject and described for each regimen (on-demand and prophylaxis).

Separate descriptive efficacy analyses of ABR will be provided for each of the following treatment regimens, assuming minimum observed period is satisfied (≥90 days):

- On-demand treatment
- Standard prophylaxis
  - ➤ continuous prophylaxis (≥46 weeks: long-term) 
  - intermittent prophylaxis (≥12 weeks-46 weeks)
  - episodic prophylaxis (<12 weeks)

  - > peri-ITI prophylaxis
- TGA-guided dosing for prophylaxis treatment
- TGA-guided dosing for on-demand treatment

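### The TGA correlations are stratified only by on-demand and prophylaxis, so TGA-guided subjects, whom the protocol separates for ABR, are pooled with the rest and can distort the coefficients

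*Protocol*

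**What the plan says.** Section 7.1 of the protocol names, among the things the study should shed light on, "the possible correlation between TGA and clinical outcome". Section 9.7.3.7 sets out the analysis: "The association between TGA parameters and bleed rates, total dose (U/kg), and the number of infusions for bleeding treatment" is to be assessed, and it "will be evaluated using a non-parametric Spearman's correlation coefficient by independent treatment regimens (on-demand and prophylaxis"). Section 9.3.4 has a matching sentence with a slightly longer list of outcomes and the same two strata: "treatment will be evaluated using a non-parametric Spearman's correlation coefficient, for both prophylaxis and on-demand treatment".

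Section 9.7.3.1 goes further for ABR. Beside on-demand treatment and standard prophylaxis it lists "TGA-guided dosing for prophylaxis treatment" and "TGA-guided dosing for on-demand treatment" as categories to be described separately. Neither 9.7.3.7 nor 9.3.4 carries that split over, and no other section leaves guided subjects out of the correlations.

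The protocol gives no TGA dosing rule and no expected number of guided subjects. TGA is recorded only where it is available (9.1.2.3, and note a to Table 2), and 9.7.3.7 rules out any formal comparison.

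**The concern.** In a subject whose dose is chosen from his TGA result, the dose is a consequence of TGA by decision. Correlating the two recovers, at least in part, the physician's practice. It does not show by itself that TGA tracks how much product the subject needs clinically. For bleed rate the distortion is of another kind. If physicians compensate for a weak thrombin response, achieved thrombin generation becomes more alike across subjects, and a real relation with bleeding looks weaker than it is.

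The protocol recognises guided dosing as distinct for ABR, then drops the distinction in the one analysis where TGA itself is a correlated variable. At stake is the reading of the TGA results. A TGA-dose coefficient could be taken as evidence that TGA reflects need when part of it is dosing practice, and a TGA-bleeding relation could be understated.

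**Working it through.** **No figure to reproduce.** The protocol states no expected correlation, power or alpha for TGA, and 9.5 says that the study size of about 55 has no statistical basis. The size of the effect can only be illustrated.

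**Inputs.**
- From the protocol: two strata (9.7.3.7, 9.3.4); guided categories in both regimens (9.7.3.1); about 55 evaluable subjects (9.5).
- Assumed: 28 subjects with TGA in one regimen (about half of 55), and a guided share from 0 to 100%, because the protocol gives neither.

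**Model**, in standardised units, with R the subject's intrinsic thrombin response and each e an independent standard normal error:
- non-guided dose: D = e, independent of R
- guided dose: D = -1.6R + 0.3e (dose goes up when response is low)
- pre-infusion TGA: R + 0.3e
- post-infusion TGA: T = R + 0.5D + 0.3e
- log bleed rate: -0.8T + 0.7e

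Mean Spearman rho over 1,500 replicates, all subjects pooled:

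| Guided share | Pre-infusion TGA v dose | Post-infusion TGA v dose | Pre-infusion TGA v bleed rate | Post-infusion TGA v bleed rate |
|---|---|---|---|---|
| 0% | 0.01 | 0.41 | -0.62 | -0.77 |
| 10% | -0.12 | 0.34 | -0.59 | -0.74 |
| 25% | -0.26 | 0.24 | -0.53 | -0.71 |
| 50% | -0.51 | 0.05 | -0.42 | -0.62 |
| 75% | -0.73 | -0.17 | -0.32 | -0.51 |
| 100% | -0.92 | -0.40 | -0.18 | -0.38 |

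**Hand check of two cells.**
- All guided, pre-infusion TGA v dose: covariance -1.6; variances 1 + 0.09 = 1.09 and 2.56 + 0.09 = 2.65; Pearson r = -1.6/√(1.09 × 2.65) = -0.94. The simulated rank correlation is -0.92.
- None guided, post-infusion TGA v dose: covariance 0.5; variances 1 + 0.25 + 0.09 = 1.34 and 1; r = 0.5/√1.34 = 0.43. The simulated rank correlation is 0.41.

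**Non-guided subjects only**, across guided shares of 10 to 75%: pre-infusion TGA v dose is about 0.00; post-infusion TGA v dose 0.37 to 0.40; pre-infusion TGA v bleed rate -0.57 to -0.63; post-infusion TGA v bleed rate -0.71 to -0.76. These hardly move with the guided share, so separating the groups removes the distortion in this model.

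**A second set of assumptions** gives similar shifts. With 25 subjects, equal follow-up, a log-SD of 0.4 in response, and guided dose inversely proportional to response but held within the general range in 9.2.1 (50 to 100 U/kg), mean rho of TGA with total prophylaxis dose is 0.00, -0.27, -0.51 and -0.89 at 0, 25, 50 and 100% guided.

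**Scale of sampling error.** The approximate 95% half-width at rho = 0 is tanh(1.96 × 1.03/√(n - 3)). For n = 28 this is tanh(2.019/5) = 0.38; for n = 14 it is tanh(2.019/3.317) = 0.54. The shift at 10% guided (0.01 to -0.12) is small beside either.

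**Follow-up length.** Total dose accumulates with time. The protocol accepts 90 days for ABR (9.7.1.2) and plans 4 years: 4 × 365.25 = 1,461 days, and 1,461/90 = 16.2. Two subjects on the same regimen could differ about 16-fold in total dose from follow-up alone.

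**The case against.** The strongest reply is that the guided share may be nil. TGA is collected only where it is routine, and the one sentence saying that TGA can individualize treatment is tied to surgery: "Thrombin generation (TG) can be used to individualize FEIBA NF treatment as a component of overall coagulation monitoring for major surgeries". The inverse dosing rule behind the figures is an assumption. All of this stands, and it is why no single size can be given. It does not remove the point, because 9.7.3.1 provides for guided dosing in both regimens with no restriction to surgery.

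It may also be said that the dose effect depends on what total dose means. The wording can be read as dose for treating bleeds, where bleed counts dominate. Under the second set of assumptions, the share of replicates in which the coefficient passes a nominal 5% cut-off, at 0, 25, 50 and 100% guided, is about 5, 29, 75 and 100% for total prophylaxis dose with equal follow-up. It is 5, 9, 17 and 47% when follow-up runs from 0.25 to 4 years, and only 4, 6, 8 and 24% for on-demand bleed-treatment dose. The large shifts therefore need prophylaxis dose and many guided subjects.

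These percentages only gauge how often the coefficient would look notable. A reader might infer an inflated type I error or lost power. The documents do not support that, because no hypothesis test is planned.

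A reader might further infer that, once guided subjects are removed, zero is the natural reference for TGA against dose. That is not so for post-infusion TGA, which rises with dose anyway (0.37 to 0.40 among non-guided subjects above).

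Finally, finer strata could be left to the analysis plan; 9.7.3.1 itself names the two regimens and then subdivides them. But 9.7.3.7 names the two and stops, so the text as written pools.

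**Conclusion.** The point holds in a limited form. As written, the TGA correlations pool guided and non-guided subjects within each regimen. To the extent that subjects are guided, the TGA-dose coefficient partly reflects dosing practice and the TGA-bleed-rate coefficient may be attenuated. In the illustrative model, the pre-infusion TGA-dose coefficient shifts by about 0.1 at a 10% guided share and about 0.5 at 50%. The bleed-rate coefficients weaken but keep their sign throughout. With no guided subjects the effect is nil. All sizes rest on the assumed dosing rule and on 25 to 28 subjects per regimen.

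A reader might go further and conclude that the correlations measure the dosing rule instead of any relation between TGA and outcome. The documents do not support that. It would be nearly true only for dose and only if almost everyone were guided, and it is not true for bleed rate. The harm is to the interpretation of a descriptive coefficient bearing on a question raised in 7.1. The descriptive TGA summaries that serve the pharmacodynamic secondary objective in 8.3 are unaffected.

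**What to change.** In 9.7.3.7, and in the matching sentence of 9.3.4:
- Within each regimen, report how many subjects or treatment periods were TGA-guided, using the categories already named in 9.7.3.1.
- Present the Spearman correlations for non-guided subjects or periods as the main result, and show guided ones separately.
- Report pre-infusion and post-infusion TGA separately.
- State that TGA-dose correlations among guided subjects describe dosing practice.
- Replace total dose by the annualized weight-adjusted dose already listed in 9.7.3.2, so that length of follow-up does not enter. This is a companion improvement and does not depend on the guidance issue.

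The dosing mode is already needed for the ABR categories, so little is added to data collection, and no clinical rule changes. The price is fewer subjects per correlation: going from 28 to 14 widens the approximate 95% half-width at rho = 0 from 0.38 to 0.54. Where a guided group is very small, listing the individual values would say more than a coefficient.

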## 9.7.3.8 Planned Interim Analysis of the Study

Only subjects that were enrolled and met all inclusion/exclusion criteria will be included in interim analyses.

The first study interim analysis is planned after all subjects are enrolled. All the following 3 interim study analyses will be available in May on annual basis in the period 2019-2021 Regular safety updates and study progress reports are to be scheduled.

## 9.8 Quality Control

## 9.8.1 Investigator's Responsibility

The investigator will comply with the protocol (which has been approved/given favorable opinion by the competent/health authority and/or EC, as applicable), ICH GCP and applicable regulatory requirements as described in the Non-interventional Trial Agreement. The investigator is ultimately responsible for the conduct of all aspects of the study at the study site and verifies by signature the integrity of all data transmitted to the responsible party. The term "investigator" as used in this protocol as well as in other study documents, refers to the investigator or authorized study personnel that the investigator has designated to perform certain duties. Sub-investigators or other authorized study personnel are eligible to sign for the investigator, except where the investigator's signature is specifically required.

#### 9.8.2 Direct Access to Source Data/Documents

The investigator/study site will cooperate and provide direct access to study documents and data, including source documentation for monitoring by the study monitor, audits by the responsible party or its representatives, review by the EC, and inspections by applicable regulatory authorities, as described in the Non-interventional Trial Agreement. If contacted by an applicable regulatory authority, the investigator will notify the responsible party of contact, cooperate with the authority, provide the responsible party with copies of all documents received from the authority, and allow the responsible party to comment on any responses, as described in the Non-interventional Trial Agreement.

#### 9.8.3 Training

The study monitor will ensure that the investigator and study site personnel understand all requirements of the protocol and his/her regulatory responsibilities as an investigator. Training may be provided at an investigator's meeting, at the study site, and/or by instruction manuals. In addition, the study monitor will be available for consultation with the investigator and will serve as the liaison between the study site and the responsible party.

## 9.8.4 Monitoring

The study monitor is responsible for ensuring and verifying that each study site conducts the study according to the protocol, standard operating procedures, other written instructions/agreements, and applicable regulatory guidelines/requirements. The investigator will permit the study monitor to visit the study site at appropriate intervals, as described in the Non-interventional Trial Agreement. Monitoring processes specific to the study will be described in the clinical monitoring plan (see Section 14.1).

## 9.8.5 Auditing

The responsible party and/or responsible party's representatives may conduct audits to evaluate study conduct and compliance with the protocol, standard operating procedures, other written instructions/agreements, ICH GCP. and applicable regulatory guidelines/requirements. The investigator will permit auditors to visit the study site, as described in the Non-interventional Trial Agreement. Auditing processes specific to the study will be described in the auditing plan (see Section 14.1).

#### 9.8.6 Non-Compliance with the Protocol

The investigator may deviate from the protocol to eliminate an apparent immediate hazard to the subject. In the event(s) of an apparent immediate hazard to the subject, the investigator will notify the responsible party immediately by phone and confirm notification to the responsible party in writing as soon as possible, but within 1 calendar day after the change is implemented. The responsible party (Baxalta) will also ensure the responsible EC is notified of the urgent measures taken in such cases according to local regulations.

If monitoring and/or auditing identify serious and/or persistent non-compliance with the protocol, the responsible party may terminate the investigator's participation. The responsible party will notify the EC and applicable regulatory authorities of any investigator termination.

#### 9.9 Limitations of the Research Methods

This prospective, uncontrolled, observational, open-label, non-interventional multicenter cohort study will provide a real-life picture on the use of FEIBA NF in patients with congenital haemophilia A or B and inhibitors. Due to the non-interventional nature of the study, the amount of data that becomes available to be entered by the investigator or designee is beyond the responsible party's control.

## 9.10 Other Aspects

This section is not applicable, as all aspects of the research method are covered by the previous sections

#### 10. PROTECTION OF HUMAN SUBJECTS

## 10.1 Compliance Statement

This study will be conducted in accordance with this protocol and applicable national and local requirements for good pharmacovigilance practices.

#### **10.2 Subject Privacy**

The investigator will comply with applicable subject privacy regulations/guidance as described in the Non-interventional Trial Agreement.

## 10.3 Ethics Committee(s) and Regulatory Authorities

Before enrollment of patients into this study, the protocol, informed consent form, any promotional material/advertisements, and any other written information to be provided will be reviewed and approved/given favorable opinion by the EC and applicable regulatory authorities. The EC's composition or a statement that the EC's composition meets applicable regulatory criteria will be documented. The study will commence only upon the responsible party's receipt of approval/favorable opinion from the EC and, if required, upon the responsible party's notification of applicable regulatory authority(ies) approval, as described in the Non-interventional Study Agreement.

If the protocol or any other information given to the subject is amended, the revised documents will be reviewed and approved/given favorable opinion by the EC and relevant regulatory authorities, where applicable. The protocol amendment will only be implemented upon the responsible party's receipt of approval and, if required, upon the responsible party's notification of applicable regulatory authority(ies) approval.

#### 10.4 Informed Consent

Investigators will choose patients for enrollment considering the study eligibility criteria. The investigator will exercise no selectivity so that no bias is introduced from this source.

All patients and/or their legally authorized representative must sign an informed consent form before entering into the study according to applicable regulatory requirements. An assent form may be provided and should be signed by patients less than 18 years of age. Before use, the informed consent form will be reviewed by the responsible parties and approved by the EC and regulatory authority(ies), where applicable, (see Section 10.3). The informed consent form will include a comprehensive explanation of the study without any exculpatory statements, in accordance with the elements required by applicable regulatory requirements. Patients or their legally authorized representative(s) will be allowed sufficient time to consider participation in the study.

By signing the informed consent form, patients or their legally authorized representative(s) agree to participate in the study, unless they withdraw voluntarily or are terminated from the study for any reason.

The responsible parties will provide to the investigator in written form any new information that significantly bears on the subjects' risks associated with medicinal product exposure. The informed consent will be updated, if necessary. This new information and/or revised informed consent form, that have been approved by the Proving (see Second) applicable EC and regulatory authorities, where applicable, will be provided by the investigator to the subjects who consent to participate in the study (see Section 9.2.4).

## 11. MANAGEMENT AND REPORTING OF ADVERSE EVENTS/ADVERSE REACTIONS

#### 11.1 Assessment of Adverse Events

Each AE from the point of enrolment until study completion will be described on the AE CRF using the medical diagnosis (preferred), or, if no diagnosis could be established at the time of reporting the AE, a symptom or sign, in standard medical terminology in order to avoid the use of vague, ambiguous, or colloquial expressions (see definitions in Section 11.2). Each AE will be evaluated by the investigator for:

- Seriousness as defined in Section 11.2.2 and Section 11.2.3
- Severity as defined in Section 11.2.4
- Causal relationship to medicinal product exposure as defined in Section 11.2.5

For each AE, the outcome (ie, recovering/resolving, recovered/resolved, recovered/resolved with sequelae, not recovered/not resolved, fatal, unknown) and action taken (ie, dose increased, dose not changed, dose reduced, drug interrupted, drug withdrawn, not applicable, or unknown) will also be recorded on the AE CRF. Recovering/resolving AEs will be followed until resolution, medically stabilized, or 30 days after the study completion/termination visit, whichever comes first.

If an investigator becomes aware of an SAE occurring in a subject after study completion, the SAE must be reported on the SAE Form within 24 hours after awareness.

